1 PROTOCOL SUMMARY

1.1 SYNOPSIS

Protocol Title:

An Exploratory Study of Nivolumab with or without Ipilimumab According to the Percentage of Tumoral CD8 Cells in Participants with Advanced Metastatic Cancer

Short Title:

Treatment with Nivolumab and Ipilimumab or Nivolumab Alone According to the Percentage of Tumoral CD8 Cells in Advanced Metastatic Cancer

Rationale:

The aim of this study is to provide a prospective classification of CD8 high (immunologically “hot”) versus CD8 low (immunologically “cold”) tumors at the time of treatment, based on the percentage of CD8 cells in a tumor biopsy, and to address the predictive value of the CD8 biomarker for selecting patients for treatment with nivolumab with or without ipilimumab.

Key Objectives and Endpoints:

Objectives	Endpoints
Primary	

To determine the clinical benefit rate (CBR) of nivolumab with or without ipilimumab in participants with advanced metastatic cancer, including advanced prostate cancer.To assess the proportion of participants in the nivolumab plus ipilimumab arm whose tumors will change from CD8 low to CD8 high as measured by a change in the percentage of tumoral CD8 cells.	
CBR is the proportion of participants who show clinical benefit, defined as CR, PR, or SD for ≥ 6 months as best response by RECIST v1.1.Change in the percentage of CD8 cells in on-treatment biopsies from baseline.
Secondary	

To determine the safety and tolerability of nivolumab with or without ipilimumab in participants with advanced metastatic cancer, including advanced prostate cancer.To determine the ORR of nivolumab with or without ipilimumab in participants with advanced metastatic cancer, including advanced prostate cancer.To assess the association of percentage of CD8 infiltration in tumor samples with clinical outcomes (ORR, PFS, and OS).	
Incidence and severity of AEs based on CTCAE v5.0.ORR: Defined as CR or PR as best response by RECIST v1.1 assessment.PFS: Defined as the time from initiation of study therapy to date of first documented progression of disease or date of death due to any cause.OS: Defined as the time from initiation of study therapy until death due to any cause.

AE = adverse event; CBR = clinical benefit rate; CR = complete response; CTCAE = Common Terminology Criteria for Adverse Events; ORR = objective response rate; OS = overall survival; PFS = progression-free survival; PR = partial response; RECIST = Response Evaluation Criteria in Solid Tumors; SD = stable disease.

Overall Design:

This is an open-label, exploratory study to evaluate nivolumab with or without ipilimumab based on percentage of tumoral CD8 cells at the time of treatment in participants with varying advanced solid tumors. Participants who have a tumor with $\geq 15\%$ CD8 cells (classified as CD8 high) will receive nivolumab monotherapy, and participants who have a tumor with $< 15\%$ CD8 cells (classified as CD8 low) will receive ipilimumab in combination with nivolumab.

Number of Participants:

A total of up to approximately 200 participants will be treated. Beginning with Amendment 2, enrollment will be limited to tumor types known to be responsive to immunotherapy, have high prevalence ($> 20\%$) CD8 $\geq 15\%$ tumors, and/or have been observed in the study to have tumors transition from CD8 low to CD8 high following initiation of immunotherapy. Beginning with Amendment 3, a total of approximately 20 participants with advanced prostate cancer and tumoral CD8 $< 15\%$ will be allocated to 1 of 2 cohorts using combinations of ipilimumab and nivolumab. Advanced prostate cancer participants with tumoral CD8 $\geq 15\%$ will be enrolled in the nivolumab monotherapy arm. Ongoing monitoring for safety and fertility will be implemented based on the method of Thall and colleagues (Thall et al, 1995) separately in the CD8 high and CD8 low tumor groups. Refer to [Section 9.1](#).

Intervention Groups and Duration:

Advanced Metastatic Cancer: Single-agent nivolumab will be administered at 360 mg intravenously (IV) every 3 weeks (Q3W). Participants who continue to show clinical benefit after the first disease assessment will receive nivolumab 480 mg IV every 4 weeks (Q4W) until progressive disease (PD) or intolerable toxicity. At PD, participants will be allowed to crossover to the CD8 low arm of ipilimumab (1 mg/kg) and nivolumab (360 mg).

For nivolumab and ipilimumab combination therapy, nivolumab will be administered at 360 mg IV Q3W, and ipilimumab will be administered at 1 mg/kg IV Q3W for the first 2 doses and then every 6 weeks for the 3rd and 4th doses, followed by nivolumab 480 mg IV Q4W until PD or intolerable toxicity. After receipt of the first dose of ipilimumab, the Investigator may determine (based on clinical symptoms) the number of future doses of ipilimumab the participant will receive, for a maximum of 4 doses. Participants who stop ipilimumab dosing early due to toxicities, may start nivolumab maintenance (ie, 4 doses [12 weeks] of nivolumab following the first dose).

Advanced Prostate Cancer (Amendment 3+): Single-agent nivolumab administered at 360 mg intravenously (IV) every 3 weeks (Q3W). Participants who continue to show clinical benefit after the first disease assessment will receive nivolumab 480 mg IV every 4 weeks (Q4W) until progressive disease (PD) or intolerable toxicity. At PD, participants will be allowed to crossover

to the advanced prostate cancer CD8 low arm of ipilimumab (5 mg/kg) and nivolumab (1 mg/kg).

For nivolumab and ipilimumab combination therapy, CD8 low arm, approximately 10 participants will be randomly allocated into 1 of 2 cohorts, using different doses of ipilimumab administered in 6-week cycles. Participants assigned to Prostate Cohort A will receive nivolumab 1 mg/kg Q3W and ipilimumab 3 mg/kg every 6 weeks (Q6W) for 2 cycles, then nivolumab maintenance 480 mg Q4W until PD or intolerable toxicity. Participants assigned to Prostate Cohort B will receive nivolumab 1 mg/kg Q3W and ipilimumab 5 mg/kg Q6W for 2 cycles, then nivolumab maintenance 480 mg Q4W until PD or intolerable toxicity. If Prostate Cohort B is determined to have a tolerable safety profile (per [Section 6.6.1.4](#)), an additional 10 participants will be enrolled to receive nivolumab 1 mg/kg Q3W and ipilimumab 5 mg/kg Q6W for 2 cycles, then nivolumab maintenance 480 mg Q4W until PD or intolerable toxicity. If the safety profile of Prostate Cohort B is deemed unacceptable, an additional 10 participants will be enrolled in Prostate Cohort A.

[figure not shown]
Safety and Futility Monitoring:

Monitoring will be ongoing during enrollment in each group to assess the stopping rules as defined in the protocol (see [Section 9.3.1](#)). There is no independent Data Safety Monitoring Committee.

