- ^a Single-agent nivolumab will be administered at 360 mg IV Q3W. Participants who continue to show clinical benefit after the first disease assessment will receive nivolumab 480 mg IV Q4W until PD or intolerable toxicity. At PD (anytime following initiation of study therapy), participants will be allowed to cross-over to the Advanced Prostate Cancer Combination Therapy Arm. All decisions to cross-over must be discussed with the Sponsor.
- ^b Blood collection prior to administration of each dose and at time of progression.
- ^c For participants who cross-over to the CD8 low arm, nivolumab will be administered at 1 mg/kg IV Q3W, and ipilimumab will be administered at 3 mg/kg IV Q6W for 2 cycles (Prostate Cohort A), followed by nivolumab maintenance 480 mg IV Q4W until PD or intolerable toxicity.

Figure 4: Study Schema: Advanced Prostate Cancer Combination Arm (CD8+ < 15% [CD8 Low Arm])

BI = baseline; Bx = tumor biopsy; DA = disease assessment; I = ipilimumab; IV = intravenous(ly); N = nivolumab; PD = progressive disease; Q3W = every 3 weeks; Q4W = every 4 weeks; Q6W = every 6 weeks; Q8W = every 8 weeks.

^a Nivolumab and ipilimumab combination therapy will be administered in 2 cohorts. For Prostate Cohort A, nivolumab will be administered at 1 mg/kg IV Q3W, and ipilimumab will be administered at 3 mg/kg IV Q6W for 2 cycles, followed by nivolumab maintenance 480 mg IV Q4W until PD or intolerable toxicity. For Prostate Cohort B, nivolumab will be administered at 1 mg/kg IV Q3W, and ipilimumab will be administered at 5 mg/kg IV Q6W for 2 cycles, followed by nivolumab maintenance 480 mg IV Q4W until PD or intolerable toxicity.

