For nivolumab and ipilimumab combination therapy in advanced prostate cancer, there will be 2 treatment cohorts, both of which will follow 6-week cycles as opposed to 3-week cycles.

Prostate Cohort A:

- nivolumab will be administered at **1 mg/kg IV Q3W** (4 doses over 2 cycles)
- ipilimumab will be administered at **3 mg/kg IV Q6W** (2 doses over 2 cycles)
- following the first 2 cycles, nivolumab will be administered at **480 mg IV Q4W** until PD or intolerable toxicity

Prostate Cohort B:

- nivolumab will be administered at **1 mg/kg IV Q3W** (4 doses over 2 cycles)
- ipilimumab will be administered at **5 mg/kg IV Q6W** (2 doses over 2 cycles)
- following the first 2 cycles, nivolumab will be administered at **480 mg IV Q4W** until PD or intolerable toxicity

Given data suggesting a dose response in earlier studies of ipilimumab 0.3, 3 and 10 mg/kg ([Wolchok et al., 2010](#)), and building on data observed in the current study with lower doses of ipilimumab, it is proposed that increased CTLA-4 inhibition in combination with anti-PD-1 may result in greater influx of CD8 T cells into an otherwise immune-excluded APC microenvironment.

The safety profile of ipilimumab has been well established in thousands of patients, both as a monotherapy at doses up to 10 mg/kg every 3 weeks, and in combination with nivolumab at various doses and schedules. In the phase 1 study CA209004 (NCT01024231), ascending doses of nivolumab (0.3, 1, or 3 mg/kg) have been studied concomitantly with ascending doses of ipilimumab (1 or 3 mg/kg) in subjects with unresectable or metastatic melanoma (Callahan et al., 2018; Wolchok et al., 2013). The combination of nivolumab 1 mg/kg + ipilimumab 3 mg/kg was assessed as the maximum tolerated dose (MTD) and taken forward for further evaluation, and was subsequently approved for treatment of metastatic melanoma (Opdivo USPI, 2020). Nivolumab 3 mg/kg + ipilimumab 3 mg/kg was found to exceed the MTD, but combinations of nivolumab 1 mg/kg with higher doses of ipilimumab have not been tested to date.

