6.1 STUDY INTERVENTION(S) ADMINISTERED

The study interventions to be administered in this study are summarized in [Table 6](#).

Table 6: Study Intervention

Study Intervention Name	Dosage Formulation	Unit Dose Strength(s)	Dosage Level(s)	Route of Administration	Sourcing
Advanced Metastatic Cancer					
Nivolumab	Aqueous solution	10 mg/mL	360 mg (administered with ipilimumab) 480 mg (maintenance)	Intravenous	Bristol-Myers Squibb
Ipilimumab	Aqueous solution	5 mg/mL	1 mg/kg (administered with nivolumab)	Intravenous	Bristol-Myers Squibb
Advanced Prostate Cancer					
Nivolumab	Aqueous solution	10 mg/mL	1 mg/kg (administered with ipilimumab) 480 mg (maintenance)	Intravenous	Bristol-Myers Squibb
Ipilimumab	Aqueous solution	5 mg/mL	3 or 5 mg/kg (administered with nivolumab)	Intravenous	Bristol-Myers Squibb

Participants with $\geq 15\%$ CD8 cells in their tumor biopsy enrolled on the CD8 high arm will be treated with single-agent nivolumab until disease progression. Additionally, participants enrolled on the CD8 high arm in this study could, at disease progression, cross-over to the CD8 low arm; participants with advanced prostate cancer enrolled under Amendment 3+ who cross-over to the CD8 low arm will be placed in Prostate Cohort A.

Nivolumab monotherapy and nivolumab in combination with ipilimumab will be administered as described below.

- *Nivolumab monotherapy (Advanced Metastatic Cancer and Advanced Prostate Cancer):* Nivolumab will be administered at 360 mg as an IV infusion over approximately 30 minutes Q3W \pm 3 days (see [Section 4.3.1](#)). Participants who

continue to show clinical benefit after the first disease assessment will receive nivolumab maintenance 480 mg IV Q4W \pm 3 days until PD or intolerable toxicity (starting at Cycle 5).

- ***Nivolumab in combination with ipilimumab (Advanced Metastatic Cancer):***

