6.6.1.4 Additional Safety Precautions (Advanced Prostate Cancer Cohort Only)

The safety profile for nivolumab (1 mg/kg) in combination with ipilimumab (3 mg/kg) is well established in melanoma and HCC at more frequent ipilimumab administration (Q3W vs Q6W) than proposed for this cohort ([Opdivo USPI, 2020](#)). Hence, concurrent enrollment will be pursued with participants allocated to regimens containing either ipilimumab 3 mg/kg or 5 mg/kg Q6W for up to 2 doses in combination with nivolumab 1 mg/kg. As the combination regimen with ipilimumab 5 mg/kg has not been extensively studied, in addition to adverse events being reviewed by the Sponsor on an ongoing basis and investigator meetings convening approximately every 2 weeks to discuss and review safety events, a safety pause is included.

Enrollment will pause until all participants have been followed for at least 6 weeks. During the pause, new participants may be consented and screened, but not initiated on study intervention. The safety pause will apply to both cohorts to preserve random allocation; however, the safety assessment as follows will apply to the ipilimumab 5 mg/kg cohort specifically. The initial 5 participants enrolled in the ipilimumab 5 mg/kg cohort will be observed for the occurrence of treatment-related adverse events (TRAEs) necessitating discontinuation of both agents (AEs requiring discontinuation are included in [Table 9](#)) from the beginning of treatment through completion of the first cycle (ie, 6 weeks).

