If 3 or fewer of the first 5 participants in the ipilimumab 5 mg/kg cohort (Prostate Cohort B) experience a TRAE leading to discontinuation of both agents, an additional 10 participants will be enrolled to receive nivolumab 1 mg/kg Q3W and ipilimumab 5 mg/kg Q6W for 2 cycles, then nivolumab maintenance 480 mg Q4W until PD or intolerable toxicity (Prostate Cohort B). If 4 or more of the first 5 participants of the ipilimumab 5 mg/kg cohort (Prostate Cohort B) experience a TRAE leading to discontinuation of both agents, an additional 10 participants will be enrolled to receive nivolumab 1 mg/kg Q3W and ipilimumab 3 mg/kg Q6W for 2 cycles, then nivolumab maintenance 480 mg Q4W until PD or intolerable toxicity (Prostate Cohort A). Only TRAEs leading to treatment discontinuation of both agents occurring up until the 5th participant in each cohort completes Cycle 1 will be included—dose delays for adverse events not otherwise meeting criteria at that time will not be counted. The stopping rule was chosen as this

corresponds to a > 80% chance that the toxicity rate in the cohort is > 40%, assuming a beta (0.8, 1.2) prior.

If either prostate cohort demonstrates 8 or greater TRAEs requiring discontinuation of therapy at any time, enrollment will be suspended until an ad hoc safety review convenes and provides a recommendation, as described above.

Table 9: Toxicity Criteria Requiring Permanent Treatment Discontinuation of Both Nivolumab and Ipilimumab (Amendment 3+ Advanced Prostate Cohort Only)

Participants should be monitored for the occurrence of any of the following AEs that are considered by the Investigator to be possibly, probably, or definitely related to ipilimumab, nivolumab, or the immunotherapy combination.
 
Treatment with all study intervention should be monitored for the occurrence of any of the following TRAEs, and if any of these events occur, action should be taken as follows:

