8.4 TREATMENT OF OVERDOSE

Overdose is defined as any dose higher than the dose specified to be administered in accordance with the protocol.

The Investigator must immediately notify the Parker Institute for Cancer Immunotherapy Pharmacovigilance Group of any occurrence of overdose with study intervention.

All overdoses should be reported as an SAE with the safety criteria of “**other important medical event.**” Details of signs and symptoms, clinical management, and outcome should be reported, if applicable. Overdoses should also be captured as protocol deviations.

The PI has the obligation to report the deviations to the IRB/IEC.

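### The Protocol Synopsis sets crossover ipilimumab for CD8-high prostate participants at 5 mg/kg, while Section 6.1 and Figure 3 set it at 3 mg/kg (Prostate Cohort A)

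*Protocol*

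**What the plan says.** The Synopsis (Protocol Section 1.1, Intervention Groups and Duration, advanced prostate cancer) allows participants on nivolumab monotherapy to cross over at progression "to the advanced prostate cancer CD8 low arm of ipilimumab (5 mg/kg) and nivolumab", with nivolumab at 1 mg/kg.

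Section 6.1 assigns the same people to a named cohort: "participants with advanced prostate cancer enrolled under Amendment 3+ who cross-over to the CD8 low arm will be placed in Prostate Cohort A". Its later bullets define Cohort A as ipilimumab 3 mg/kg and Cohort B as 5 mg/kg, each with nivolumab 1 mg/kg. Figure 3 footnote c states the crossover regimen directly: "ipilimumab will be administered at 3 mg/kg IV Q6W for 2 cycles (Prostate Cohort A), followed by nivolumab maintenance".

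Figure 3 footnote a permits crossover at progression at any time after therapy starts and adds a safeguard: "All decisions to cross-over must be discussed with the Sponsor".

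**The concern.** A participant cannot receive both regimens, and the documents do not rank the Synopsis against Section 6.1. A site planning from the Synopsis would prepare 5 mg/kg; a site planning from Section 6.1 would prepare 3 mg/kg.

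The difference matters because the higher dose is the experimental one. Section 4.3.2.1 reports that nivolumab 1 mg/kg with ipilimumab 3 mg/kg was the maximum tolerated dose in a phase 1 melanoma study, and that "combinations of nivolumab 1 mg/kg with higher doses of ipilimumab have not been tested to date". Section 6.6.1.4 therefore puts the 5 mg/kg cohort under a safety pause and a decision rule. The Synopsis sentence gives the same dose to crossover participants with no reference to that rule.

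**Working it through.** The check is mainly a comparison of every place that sets the crossover dose or cohort for CD8-high prostate participants.

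| Place | Crossover ipilimumab |
|---|---|
| Protocol 1.1 Synopsis | 5 mg/kg |
| Protocol 1.2, Figure 3 footnote c | 3 mg/kg, Cohort A |
| Protocol 6.1 | Cohort A, defined in the same section as 3 mg/kg |
| SAP 3 | 3 mg/kg |
| SAP 8.1 (copy of the Synopsis) | 3 mg/kg |

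Four of the five support 3 mg/kg, and the Synopsis is the exception. The two SAP entries carry less weight, because the SAP's prostate text describes the design before Amendment 5 (all 20 CD8-low participants randomized, 10 per arm). The contradiction stands on the Protocol alone. Protocol Sections 4.3.1 and 7.1 also allow ipilimumab to be added, or crossover, at progression, but give no dose.

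**Is one text simply newer?** The Synopsis paragraph and the Section 6.1 sentence both carry the Amendment 3+ label. The Amendment 5 summary describes changes to CD8-low allocation and lists no change of crossover dose.

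**Does any precedence rule settle it?** Protocol Section 9.4 lets the SAP supersede the Protocol, but for statistical analyses. No rule covers dosing.

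**Size of the difference:**
- Per infusion: 5 / 3 = 1.67, so 67% higher.
- Over the two planned doses: 2 × 5 = 10 mg/kg against 2 × 3 = 6 mg/kg.
- For scale, the metastatic castration-resistant prostate cancer regimen in Section 2.2.3 gives ipilimumab 3 mg/kg for up to 4 cycles: 4 × 3 = 12 mg/kg at most. The 10 mg/kg total is below this, so the issue is the per-infusion dose given with nivolumab, not cumulative exposure.

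**Link to the Cohort B decision.** The rule in Section 6.6.1.4 that sends the next 10 participants to Cohort A opens "If 4 or more of the first 5 participants of the ipilimumab 5 mg/kg cohort (Prostate Cohort B) experience a TRAE" causing discontinuation of both agents, which is 4 / 5 = 80%. Read literally, the Synopsis crossover dose would stay at 5 mg/kg even then. The pause is worded for new entrants: "During the pause, new participants may be consented and screened, but not initiated on study intervention". It does not mention participants already on study who cross over.

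**Consequence if Section 6.1 governs.** Section 8.4 states: "Overdose is defined as any dose higher than the dose specified to be administered in accordance with the protocol". It requires every overdose to be reported as an SAE and recorded as a deviation, so following the Synopsis would produce both.

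**The case against.** The strongest reply is that this is one phrase in a summary. The section that sets administration and the schema footnote agree with each other, and most readers would follow them over a synopsis. The Sponsor hears of every crossover before it happens. The documents give no count of CD8-high prostate participants, but Section 2.2.3 describes prostate tumors as immunologically cold, so there are probably few. These points lower the chance of an error. They do not tell a site or the Sponsor's contact which dose is right, and a dosing error harms the individual treated however few are exposed.

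Four narrower points have some force:

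- **Overdose.** Section 10.5.5 defines overdose against the dose being studied and says it is not in itself an adverse event. Since 5 mg/kg is studied in Cohort B, the overdose consequence holds only under Section 8.4, and only if Section 6.1 governs.
- **Pause.** Section 6.6.1.4 also says enrollment pauses, and Section 7.1 describes crossover as enrolling into the combination arm. The pause could therefore be read to cover crossover participants. The text leaves this open.
- **Other safety controls.** Safety events are reviewed continuously and at investigator meetings about every two weeks, and enrollment is suspended if either prostate cohort reaches 8 treatment-related events requiring discontinuation. These are real protections, but none sets the crossover dose.
- **Strength of the evidence gap.** Section 6.6.1.4 says only that the 5 mg/kg combination has not been extensively studied, and the plan itself may treat 5 + 10 = 15 participants at that dose. Those participants come under the decision rule, however; the Synopsis crossover dose is not tied to it.

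**Conclusion.** The Protocol is wrong as written. Current text gives the same participants two ipilimumab doses that differ by 67% per infusion, and the Synopsis gives the higher one without tying it to the Cohort B safety decision. On the weight of the text, 3 mg/kg (Prostate Cohort A) is the intended regimen. That is an inference from agreement among the other sections, and only the Sponsor can confirm it. The number of participants exposed is unknown and probably small, and no estimate, interval or sample size is affected. The correction is still needed, because the error concerns the dose a patient receives of a combination that the Protocol says is untested above 3 mg/kg.

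**What to change.** In the Synopsis, change the prostate crossover regimen to ipilimumab 3 mg/kg with nivolumab 1 mg/kg, and name Prostate Cohort A so that it matches Section 6.1 and Figure 3 footnote c. Notify sites of the correct dose.

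If the Sponsor did intend 5 mg/kg, change Section 6.1, Figure 3 footnote c and SAP Sections 3 and 8.1 instead. In that case, allow crossover at 5 mg/kg only after Cohort B has been found tolerable under Section 6.6.1.4, and state how the pause applies to crossover participants.

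The first option changes one phrase and leaves sample size, data collection and analysis untouched. It may need IRB/IEC approval under Section 10.1.2, since a change to a stated dose is not clearly administrative. That cost is small against the risk.
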